##### Serious adverse event

Proprietary confidential information.

© 2018 Boehringer Ingelheim International GmbH or one or more of its affiliated companies. All rights reserved.

This document may not - in full or in part - be passed on, reproduced, published or otherwise used without prior written permission.

A serious adverse event (SAE) is defined as any AE which results in death, is immediately life-threatening, results in persistent or significant disability / incapacity, requires or prolongs patient hospitalisation, is a congenital anomaly / birth defect, or is to be deemed serious for any other reason if it is an important medical event when based upon appropriate medical judgement which may jeopardise the patient and may require medical or surgical intervention to prevent one of the other outcomes listed in the above definitions.

**Intensity of adverse event**

The intensity of adverse events should be classified and recorded according to the Common Terminology Criteria for Adverse Events (CTCAE) version 4.0 and recorded in the eCRF.

**Causal relationship of adverse event**

Medical judgment should be used to determine the relationship, considering all relevant factors, including pattern of reaction, temporal relationship, de-challenge or re-challenge, confounding factors such as concomitant medication, concomitant diseases and relevant history. Assessment of causal relationship should be recorded in the case report forms (CRF).

Yes: There is a reasonable causal relationship between the investigational product administered and the AE.

No: There is no reasonable causal relationship between the investigational product administered and the AE.

**Worsening of the underlying disease or other pre-existing conditions**

Disease Progression in oncology trials is a study endpoint for analysis of efficacy. Disease progression is exempted from reporting as a (S)AE. Progression of the patient's underlying malignancy will be recorded in the appropriate pages of the (e)CRF as part of efficacy data collection. Death due to disease progression is to be recorded on the appropriate (e)CRF page and not on a SAE form.

Examples of exempted events of PD are: Progression of underlying malignancy (Progressive disease PD): if PD is clearly consistent with the suspected progression of the underlying malignancy as defined by the respective response criteria.

- Hospitalization/Procedures due solely to the progression of underlying malignancy (PD)
- Clinical symptoms and/or signs of progression (with or without confirmation by objective criteria e.g. imaging, clinical measurement): if the symptom can exclusively be determined to be due to the progression of the underlying malignancy and does not meet the expected pattern of progression for the disease under study.

When there is evidence suggesting a causal relationship between the drug and the progression of the underlying disease, the event must be reported as (S)AE on the eCRF and SAE form.

Worsening of other pre-existing conditions will be recorded as an (S)AE in the eCRF and SAE form (if applicable).

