#### 5.2.2.2 Adverse event and serious adverse event reporting

All adverse events, serious and non-serious, occurring during the course of the clinical trial (i.e., from signing the informed consent onwards through the follow-up period of 28 days after the last drug administration, [Table 5.2.2.2:1](#)) will be collected, documented and reported to the sponsor by the investigator on the appropriate eCRFs / SAE reporting forms. Reporting will be done according to the specific definitions and instructions detailed in the 'Adverse Event Reporting' section of the Investigator Site File.

For each adverse event, the investigator will provide the onset date, end date, intensity, treatment required, outcome, seriousness, and action taken with the investigational drug. The investigator will determine the relationship of the investigational drug to all AEs as defined in [Section 5.2.2.1](#).

The Residual Effect Period (REP), defined as the period of time after the last dose of medication when measurable drug levels or pharmacodynamic effects are still likely to be present, is 28 days for Afatinib. All events reported within 28 days of the last study medication will be considered on-treatment.

The investigator does not need to actively monitor patients for adverse events once the clinical trial has ended. However, if the investigator becomes aware of an SAE that occurred after the patient has completed the clinical trial, it should be reported by the investigator to the sponsor if considered relevant by the investigator.

All AEs, including those persisting after end of study treatment must be followed up until they have resolved or have been sufficiently characterized or the principal investigator decides to not further pursue them.

Table 5.2.2.2:1 AE/SAE reporting requirements

Time period	Reporting requirements
For screen failures; From signing of informed consent to the timepoint where ineligibility is	Report all AEs and SAEs. This includes all

Proprietary confidential information.

© 2018 Boehringer Ingelheim International GmbH or one or more of its affiliated companies. All rights reserved.

This document may not - in full or in part - be passed on, reproduced, published or otherwise used without prior written permission.

confirmed	deaths.

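### One example of progression events exempt from (S)AE reporting requires an unexpected pattern of progression, which runs opposite to the first example in the same list

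*Protocol*

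**What the plan says.** The text is in Protocol Section 5.2.2.1, under worsening of the underlying disease. The general rule is: "Disease progression is exempted from reporting as a (S)AE". Three examples of exempted events follow.

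- **First example, progressive disease itself:** exempt "if PD is clearly consistent with the suspected progression of the underlying malignancy as defined by the respective response criteria".
- **Second example, hospital stays and procedures:** exempt when progression is the only reason for them.
- **Third example, clinical symptoms or signs of progression:** these qualify "with or without confirmation by objective criteria e.g. imaging, clinical measurement". The symptom must be attributable exclusively to progression of the "underlying malignancy and does not meet the expected pattern of progression for the disease under study".

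The section then brings one kind of event back into reporting: where there is "evidence suggesting a causal relationship between the drug and the progression of the underlying disease, the event must be reported as (S)AE".

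Section 5.2.2.2 sets the general duty to report AEs. It adds that "The investigator will determine the relationship of the investigational drug to all AEs" and refers sites to the Investigator Site File: "Reporting will be done according to the specific definitions and instructions detailed in the" adverse event section of that file. Neither Section 5.2.2.2 nor its Table 5.2.2.2:1 mentions the progression exemption or the pattern of progression.

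**The concern.** The first and third examples attach conditions that point in opposite directions. The first exempts an event because it looks like progression. The third exempts a symptom that does not look like the expected progression, provided the investigator attributes it to progression.

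An unexpected pattern is a reason to question that attribution. The protocol's own guidance on causal relationship, also in Section 5.2.2.1, lists the pattern of reaction among the factors to weigh. A rule meant to keep ordinary tumour progression out of the safety data should not select the cases where progression is least convincing.

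What is at stake is the capture of an atypical event, possibly drug-related, that is wrongly put down to the cancer. If it is treated as exempt:

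- no AE is recorded, so the causality assessment required for AEs is not called for;
- no SAE form goes to the sponsor within 24 hours, even if the event is serious;
- the event is missing from the tables planned in Protocol Section 7.3.3.3 and SAP Section 7.8.1, including all AEs, SAEs and AEs leading to death;
- the deviation review under code C2 in SAP Table 6.2:1 would not find it, because that review starts from reported dose changes and AEs.

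**Working it through.** No arithmetic applies: the point depends on no rate, sample size or error level. The check sets the conditions side by side and then looks for any other text that corrects the third example.

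**1. Direction of each condition**

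| Text in Section 5.2.2.1 | Condition for exemption | Refers to pattern? |
|---|---|---|
| General rule | Event is disease progression | No |
| First example | Clearly consistent with suspected progression, by response criteria | Yes: must fit |
| Second example | Due solely to progression | No |
| Third example | Exclusively due to progression, and expected pattern not met | Yes: must not fit |

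The first and third examples concern different objects: progression by response criteria, and symptoms with or without objective confirmation. This is therefore not a strict logical contradiction. It is a reversal of direction within one list that serves one purpose.

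**2. What the third example does when read literally**

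| Investigator's judgement | Pattern | Third example as written | Third example if aligned with the first |
|---|---|---|---|
| Exclusively progression | Expected | Not covered by the example | Exempt |
| Exclusively progression | Unexpected | Exempt | Reported |
| Not exclusively progression | Either | Not exempt | Not exempt |

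The first row has little practical consequence. The bullets are examples, so a typical symptom of progression can still be exempt under the general rule. The second row carries the risk.

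**3. Does other text correct it?**

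- *Return clause, same section.* It covers suspicion that the drug caused the progression. It does not reach an event that is not progression at all but is labelled as such.
- *Changes in vital signs, ECG, physical examination and laboratory results (Section 5.2.2.1), and additional laboratory evaluations (Section 5.2.3).* Clinically relevant changes, and abnormal findings from additional tests, are to be recorded as AEs. This narrows the gap for events with objective findings, but not for events that are symptoms only.
- *Assessment for interstitial lung disease (Sections 4.2.1.2 and 4.4.1).* Acute or worsening respiratory symptoms must be evaluated whatever their reporting category. This is a clinical safeguard and does not settle whether the symptom is reported.
- *Section 5.2.2.2 and Table 5.2.2.2:1.* They require all AEs to be reported, but do not say how the exemption or an unexpected pattern is handled.
- *Investigator Site File.* It may contain clearer instructions, but it is not among the documents.

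None of the available text corrects the clause.

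**4. Effect on the endpoints**

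- *Primary endpoint and time to first dose reduction.* Both need an AE that led to a dose reduction. Section 4.4.1 says that unrelated events should not lead to one, so a symptom attributed wholly to the tumour should not enter either endpoint.
- *The four grade 3 or higher endpoints* (diarrhoea, rash/acne, stomatitis, paronychia). The protocol already describes these as afatinib effects, so attribution to progression is unlikely.

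That accounts for the primary endpoint and all 4 + 1 = 5 secondary endpoints, with little or no effect expected on any of them.

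**The case against.** The strongest reply is that the clause does not exempt a misattributed event. It also requires that the symptom be exclusively due to progression, and a drug effect mistaken for progression does not meet that on its true facts. The failure would be one of clinical judgement, which no wording removes. This is correct, and it limits the point: harm needs an error of attribution. But investigators apply the rule to what they believe at the time. Wording that treats an unexpected pattern as grounds for exemption, when it should prompt doubt, makes the error easier to leave uncorrected.

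A second reply is that the *not* is an obvious slip that sites will read past. That may be so, but it is an inference. The sponsor should confirm the intended meaning, as this is current text in a rule that sites follow.

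Three stronger readings are tempting, and the documents do not support them.

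- *The third example contradicts the general exemption.* The general rule says nothing about pattern, so there is nothing in it to oppose. The mismatch is with the first example only.
- *The protocol also contradicts itself on deaths.* Table 5.2.2.2:1 asks for all deaths to be reported, while Section 5.2.2.1 says: "Death due to disease progression is to be recorded on the appropriate (e)CRF page and not on a SAE form". The table row names no form, and Section 5.2.2.2 allows reporting on eCRFs or SAE forms as appropriate. The two read together as a specific rule within a general one.
- *The safety results are materially biased.* Nothing in the documents shows that any event was affected or how often one might be. One patient's share of a table of about 25 would describe the table, not this defect.

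**Conclusion.** The point holds as a defect of wording in an operative safety-reporting rule. The symptoms example makes an unexpected pattern a condition for exemption, which reverses the first example, and no other available text corrects it.

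Its size is small. The consequence is confined to an atypical symptom that is misjudged as exclusively due to progression and is not caught through objective findings. Such an event would be missing from the AE, SAE or fatal-AE tables and would get neither a causality assessment nor expedited reporting. The frequency cannot be estimated from the documents.

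The conclusion rests on a literal reading of the clause and on the assumption that the Investigator Site File does not already override it. Confidence is high for the wording and lower for any practical effect. This is a minor correction, worth making because accurate safety capture is the purpose of the trial.

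**What to change.** Reword the symptoms example to agree with the first: a symptom or sign is exempt only if it is judged exclusively due to progression *and* is consistent with the expected pattern of progression for the disease. State expressly that a symptom failing either condition is reported as an (S)AE. The express statement is needed because the bullets are only examples, and the general rule alone could still be read as exempting anything labelled progression.

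Send sites a short clarification, and align the Investigator Site File if it repeats the clause.

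The cost is one clause and one site communication. A check of progression and death eCRF entries before database lock is optional. With about 25 patients at about 15 to 20 sites it would be small, although some entries might need source queries, since exempted symptoms are not on the AE pages.

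The rewording does not help with a typical-looking event wrongly attributed to progression. That still depends on the investigator's judgement.

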### Changes in vital signs, ECG, physical examination, and laboratory test results

Changes in vital signs, ECG, physical examination and laboratory test results will be recorded as an (S)AE in the eCRF, if they are judged clinically relevant by the investigator.

### Adverse Event of Special Interests (AESIs)

No AESIs have been defined for this trial.

### Expected Adverse Events

For expected (listed) AEs of afatinib, see the current version of the IB (Investigator's Brochure) ([U03-3218-13](#)).

#### 5.2.2.2 Adverse event and serious adverse event reporting

All adverse events, serious and non-serious, occurring during the course of the clinical trial (i.e., from signing the informed consent onwards through the follow-up period of 28 days after the last drug administration, [Table 5.2.2.2:1](#)) will be collected, documented and reported to the sponsor by the investigator on the appropriate eCRFs / SAE reporting forms. Reporting will be done according to the specific definitions and instructions detailed in the 'Adverse Event Reporting' section of the Investigator Site File.

For each adverse event, the investigator will provide the onset date, end date, intensity, treatment required, outcome, seriousness, and action taken with the investigational drug. The investigator will determine the relationship of the investigational drug to all AEs as defined in [Section 5.2.2.1](#).

The Residual Effect Period (REP), defined as the period of time after the last dose of medication when measurable drug levels or pharmacodynamic effects are still likely to be present, is 28 days for Afatinib. All events reported within 28 days of the last study medication will be considered on-treatment.

The investigator does not need to actively monitor patients for adverse events once the clinical trial has ended. However, if the investigator becomes aware of an SAE that occurred after the patient has completed the clinical trial, it should be reported by the investigator to the sponsor if considered relevant by the investigator.

All AEs, including those persisting after end of study treatment must be followed up until they have resolved or have been sufficiently characterized or the principal investigator decides to not further pursue them.

Table 5.2.2.2:1 AE/SAE reporting requirements

Time period	Reporting requirements
For screen failures; From signing of informed consent to the timepoint where ineligibility is	Report all AEs and SAEs. This includes all

Proprietary confidential information.

© 2018 Boehringer Ingelheim International GmbH or one or more of its affiliated companies. All rights reserved.

This document may not - in full or in part - be passed on, reproduced, published or otherwise used without prior written permission.

confirmed	deaths.
For treated patients; From signing of informed consent to the end of the follow-up visit (28 days after last trial drug administration)	Report all AEs and SAEs regardless of relatedness or whether the trial drug is administered. This includes all deaths.
After the 28 day followup visit until vital status followup (VS) is completed	Report all related SAEs.
After the patient has completed the study	Active monitoring for adverse events is not required. If the investigator becomes aware of an SAE that occurred after the patient has completed the clinical trial it should be reported to the sponsor if considered relevant by the investigator.

If not stipulated differently in the ISF, the investigator must report the following events using the SAE form via fax immediately (within 24 hours) to the sponsor: SAEs and non-serious AEs relevant to an SAE. The same timeline applies if follow-up information becomes available. In specific occasions, the investigator could inform the sponsor via telephone. This does not replace the requirement to complete and fax the BI SAE form.

BI has set up a list of AEs which are defined to be always serious. In order to support the investigator with the identification of these “always serious adverse events”, if a non-serious AE is identified to be serious per BI definition, a query will be raised. The investigator must verify the description and seriousness of the event. If the event description is correct, the item “serious” needs to be ticked and an SAE has to be reported in expedited fashion following the same procedure as above.

The list of these adverse events can be found via the Remote Data Capture (RDC) system.

With receipt of any further information to these events, a follow-up SAE report has to be provided. SAEs and non-serious AEs must include a causal relationship assessment made by the investigator.

The SAE form is to be forwarded to the defined unique entry point identified for the BI OPU (operative unit) (country-specific contact details will be provided in the Investigator Site File). This immediate report is required irrespective of whether the investigational product has been administered or not and irrespective of causal relationship. It also applies if new information to existing SAEs becomes available.

### Pregnancy

In this study, pregnancy is not expected to occur in female participants with the age of 70 years or older. In rare cases, pregnancy might occur in a female partner of a male participant with drug exposure to afatinib; in which case, pregnancy must be reported following BI internal SOP using the pregnancy monitoring form (refer to ISF).

Proprietary confidential information.

© 2018 Boehringer Ingelheim International GmbH or one or more of its affiliated companies. All rights reserved.

This document may not - in full or in part - be passed on, reproduced, published or otherwise used without prior written permission.

### 5.2.3 Assessment of safety laboratory parameters

Safety laboratory samples will be analysed at the investigator's local laboratory. Safety laboratory examinations will include hematology, biochemistry and urine examinations.

Table 5.2.3: 1 Laboratory tests to be performed

Category	Parameters
Hematology	Hemoglobin, hematocrit, platelet count, white blood cell count (WBC), with differential (neutrophils and bands)
Coagulation*	International Normalized Ratio (INR), activated Partial Thromboplastin Time (aPTT)
Chemistry	
Electrolytes	Sodium, potassium, calcium, magnesium, chloride, bicarbonate ( $\text{HCO}_3$ )
Liver function tests	Alkaline phosphatase, aspartate aminotransferase (AST), alanine aminotransferase (ALT), $\gamma$ -glutamyltransferase (GGT), total bilirubin

Table 5.2.3: 1 Laboratory tests to be performed (continued)

Category	Parameters
Renal function parameters	Blood urea nitrogen (BUN), creatinine; Creatinine clearance (see Appendix 10.3 )
Other	Glucose, albumin
Urinalysis*	The following will be tested at baseline and at the EOT visit: pH, protein, glucose, ketones, blood, leucocytes, nitrite, bilirubin, urobilinogen, and specific gravity. In case of pathological finding further evaluation should be performed and results documented

\* tested at Screening and EOT only

The investigator should complete additional evaluations of laboratory tests as clinically indicated. Any abnormal findings from these investigations need to be reported as an Adverse Event.

Proprietary confidential information.

© 2018 Boehringer Ingelheim International GmbH or one or more of its affiliated companies. All rights reserved.

This document may not - in full or in part - be passed on, reproduced, published or otherwise used without prior written permission.

## 5.2.4    **Electrocardiogram**

Electrocardiogram (ECG) is only required at screening. If any additional ECG is performed as part of routine clinical care and clinically significant results are found, this will be documented in accordance with the adverse event process.

## 5.2.5    **Assessment of other safety parameters**

### 5.2.5.1 Physical examination, vital signs, height and weight

A full physical exam must include cardiopulmonary examination, examination of the regional lymph nodes, and examination of the abdomen and an assessment of the mental and neurological status. Additional symptoms which have not been reported during a previous examination must be clarified. Wherever possible the same investigator should perform this examination.

A complete physical examination will be done at Screening, on Day 1 of each treatment course and at the End of Treatment visit. A symptom-directed examination is to be performed at all other visits.

### 5.2.5.2 Vital Signs

Vital sign measurements should include blood pressure [systolic blood pressure, diastolic blood pressure], pulse rate, respiratory rate, temperature and measurement of height (in cm, at screening) and body weight (in kg at screening and end of trial). Evaluation of the ECOG PS (see [Appendix 10.1](#)) will be performed at the times specified in the [Flowchart](#).

questionnaire that each contains several short measurement tools. In the final GAM,

